#### **2.2.4 Hospitalization of People with COVID-19**

Countries and jurisdictions differ in the clinical management of COVID-19 patients. Early in the epidemic, faced with small numbers of infected persons, some resource-rich countries such as Singapore elected to admit all persons with COVID-19 illness regardless of symptom severity to facilitate strict isolation. Admission for reasons of public health or quarantine, rather than medical management, continues to be a requirement in some countries notably in Asia. Elsewhere, it is more common for those with mild illness to be advised to self-isolate at home, while only those severely unwell are admitted for medical management.

Thresholds for ICU management also differ globally and are likely to vary significantly even within individual countries at different stages of the epidemic. For example, at the epidemic peak procedures commonly performed only in ICU may be extended to other care areas, while patients who might otherwise have been considered for ICU admission may be palliated if clinical services are overwhelmed.

Reported mortality rates for those who develop end-organ failure requiring intensive support, including those admitted to ICU, differ widely. Amongst 1591 ICU patients from the Lombardy region in Italy, hardest hit by COVID-19, 88% required mechanical ventilation and 11% noninvasive ventilation. The ICU mortality rate was 26%. Of 1043 patients with available data, 709 (68%) had at least 1 comorbidity and 509 (49%) had hypertension, 21% had cardiovascular disease. Younger patients ( $\leq 63$  years) compared to older patients, had lower ICU mortality and higher rates of discharge from ICU. The median length of stay in the ICU was 9 days though 58% remained in ICU at time of report. In one report of the Chinese experience in Wuhan, 31 of 32 persons who required mechanical ventilation died. In the United Kingdom, of the 4078 COVID-19 patients admitted into critical care with reported outcomes, 50.7% died in ICU; those requiring advanced respiratory support and renal support had worse outcomes. These data underline the importance of attenuating the disease in its early phase prior to the development of end-organ failure and the requirement of intensive care.

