## 4.2 Secondary Objectives

Secondary objectives will be assessed by comparing hIVIG + SOC with placebo + SOC over the 28 day follow-up period for outcomes listed below. Because there is no established endpoint for evaluating the clinical efficacy of treatments for COVID-19, other clinically relevant outcomes, including outcomes used in other COVID-19 treatment trials, will be recorded. Thus, the randomized groups can be compared for multiple outcomes, and results can be compared or combined with other trials. Many of the endpoints used in other trials are ordinal outcomes or are defined based on a dichotomy of an ordinal outcome and assessed at a single follow-up time point or as a time-to-event outcome.

1. All-cause mortality through Day 28.
2. The primary ordinal outcome on Days 3, 5, 14 and 28.
3. Change in National Early Warning Score (NEWS) (see [Appendix G](#)) from baseline at Day 3.
4. Time to the 3 least favorable categories of the primary outcome measure.
5. Time to the 2 most favorable categories of the primary outcome measure.
6. Hospitalization status (a binary outcome, alive and discharged from the hospital to home or rehabilitation versus dead or hospitalized) at Days 7, 14 and 28.
7. Time to discharge (this is similar to the recovery outcome used in the ACTT-1 trial)

8. Days alive outside of a hospital through Day 28
9. Pulmonary only components of the primary outcome measure at Days 3, 5, 7, 14 and 28
10. Thrombotic components of the primary outcome measure (stroke, myocardial infarction, venous and arterial thrombosis or embolism, plus disseminated intravascular coagulation) at Days 3, 5, 7, 14, and 28.
11. Outcomes assessed in other treatment trials of COVID-19 for hospitalized participants in order to facilitate cross trial comparisons and overviews, e.g., 6-, 7- and 8- category ordinal scales at days 7, 14 and 28; and binary outcomes defined by improvement or worsening based on the primary ordinal outcome and ordinal outcomes used in other trials.
12. Clinical organ dysfunction defined by *new onset* of any one or more of the following conditions (or requirement for the following therapies) through Day 28:
  - a. Respiratory:
    1. Extracorporeal membrane oxygenation (ECMO)
    2. Invasive ventilation
    3. Non-invasive ventilation or high flow oxygen
  - b. Cardiac and vascular:
    1. Myocardial infarction
    2. Myocarditis or pericarditis
    3. NYHA Class III/IV congestive cardiac failure

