    4. Vasopressor therapy
  - c. Renal:
    1. Renal replacement therapy (dialysis)
  - d. Hepatic:
    1. Hepatic decompensation
  - e. Neurological
    1. Cerebrovascular event (stroke)
    2. Encephalitis, meningitis or myelitis
    3. Acute delirium
  - f. Hematological:
    1. Disseminated intravascular coagulation
    2. New thrombotic events, including pulmonary embolism, deep venous thrombosis, or arterial thrombosis
  - g. Infective:
    1. Microbiologically-proven severe infection (not including SARS-CoV-2)
13. Safety and tolerability will be assessed using outcomes described above (e.g., mortality and thrombotic outcomes) and also assessed by the following outcomes:

- a. A composite of incident grade 3 and 4 events (not limited to a laboratory abnormality), SAEs (see Section 10.1.2), or death through Day 7 (primary safety endpoint)
  - b. Infusion reactions of any grade severity during the infusion and 2 hours post-infusion, and percentage of participants for whom the infusion was interrupted or stopped prior to completion
  - c. SAEs or deaths through Day 28
  - d. Prevalence of adverse events of any grade on Days 1, 3, 7 and 28.
14. Change in immunoglobulin levels (IgG, IgG subclasses, IgM, IgA) and neutralizing antibody titers from baseline to Days 1, 2, 3, 7, 28 and 90.

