### 5.5.3 Key secondary outcomes

The study is not powered to detect treatment differences in mortality, because the mortality is expected to be low given the eligibility criteria.

The following outcomes are defined as key secondary outcomes:

**Composite of death, end-organ failure, or life-threatening end-organ dysfunction (categories 5-7 of the ordinal outcome) at Day 7:** This composite outcome comprises the most severe three categories of the ordinal outcome. Decreasing the probability that a participant enters one of these disease states and remains there through Day 7, has high clinical significance. Comparing the hVIG+SOC versus the placebo+SOC groups for the proportion of participants in the three worst categories on Day 7, a total sample size of 500 participants is sufficient to detect a decrease to 6.1% in the hVIG group compared with 13.6% in the placebo group (difference 7.5%, OR=2.4) with 80% power, under the following assumptions:

- a. The analysis will be intention to treat.
- b. Type 1 error = 0.05 (2-sided) and power = 0.80.
- c. The proportion of participants who are in categories 5-7 of the ordinal outcome on Day 7 in the placebo + SOC group is 13.6% (Table 1). In the ACTT-1 study, the proportion was 10.8%, among participants in baseline categories 4+5 of the ACTT-1 ordinal outcome who were randomized to the remdesivir group (confidential data, personal communication).

A decrease from 13.6% to 8% (OR 1.8) could be detected with power of 47%.

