## 7.4 Secondary Outcomes

The protocol defines a number of secondary endpoints in addition to the two key endpoints described in the previous section. These analyses will be carried out for the final report. No adjustment for multiplicity for all the treatment comparisons for the secondary outcomes will be made; they are supportive to the primary endpoint analysis.

Selected secondary endpoints may also be analyzed for the interim monitoring report to help evaluate the safety and efficacy of hVIG.

*Multiple imputation will only be used for data missing on the primary endpoint; all secondary endpoints will use complete case.*

Below, the secondary outcomes from the protocol are cited, with a short description of the analysis methods. The secondary outcomes are grouped by analysis methods and are not listed in order of importance.

1. The primary ordinal outcome on Days 3, 5, 14 and 28.
2. Pulmonary only components of the primary outcome measure at Days 3, 5, 7, 14 and 28
3. Thrombotic components of the primary outcome measure (stroke, myocardial infarction, venous and arterial thrombosis or embolism, plus disseminated intravascular coagulation) at Days 3, 5, 7, 14, and 28.
4. Clinical organ dysfunction
5. The ordinal outcome similar to the one used in the ACCT trial of remdesivir will be used to compare treatment groups at Day 7. The ACCT ordinal outcome included 8 categories. We can only approximate the categories because data were not collected concerning hospitalization for infection-control reasons. It is similar to the ITAC primary ordinal outcome but

considers hospitalization status. The following 8 categories will be defined for this ordinal outcome:

- Not hospitalized, no limiting symptoms due to COVID-19
- Not hospitalized, limiting symptoms due to COVID-19, home oxygen requirement, or both
- Hospitalized, no limiting symptoms due to COVID-19, not requiring supplemental oxygen
- Hospitalized, limiting symptoms due to COVID-19, not requiring supplemental oxygen
- Hospitalized, requiring any supplemental oxygen
- Hospitalized, requiring non-invasive ventilation or use of high-flow oxygen devices.
- Hospitalized, requiring invasive mechanical ventilation or ECMO
- Death

6. Percentage in 2 most favorable categories at Day 7.
7. Hospitalization status at Days 14 and 28.

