8. Hospitalization status (a binary outcome, alive and discharged from the hospital to home or rehabilitation OR able to independently undertake usual activities with minimal or no symptoms versus dead or hospitalized AND unable to independently undertake usual activities) at Days 7, 14 and 28.

*For outcomes 1-8, the proportion of participants in each category will be summarized by treatment group. For the ordinal outcomes, a summary OR will be estimated using a cumulative logistic regression model which includes a single indicator for treatment, indicators for the participant's clinical state at entry (categories of ordinal outcome), its two-way interactions with the six cutoffs for each of the six cumulative odds of improvement, indicators for which of the four study product/matching placebo group was used and their two-way interactions with the six cutoffs. For the binary outcomes, a summary OR will be estimated using a logistic regression model which includes a single indicator for treatment, indicators for the participant's clinical state at entry (categories of ordinal outcome), and indicators for which of the four study product/matching placebo group was used. For interim analyses we will consider clinical organ dysfunction as a binary composite endpoint at Day 7 and Day 28. At the end of the trial we will take into account the severity of each organ dysfunction by developing a weighting scheme by examining the pooled association of each item with subsequent death.*

9. All-cause mortality through Day 28.
10. Time to the three least favorable categories of the primary outcome measure.

*For outcomes 9 and 10, the cumulative incidence of death (outcome 9) or the three least favorable categories (outcome 10) by treatment group will be estimated using Kaplan-Meier methods. The treatment groups will be compared using a log-rank test. A summary HR comparing the treatment groups will be estimated using a Cox proportional hazards model. These models will be stratified by study product/matching placebo group and baseline ordinal outcome group.*

11. Time to the two most favorable categories of the primary outcome measure.
12. Time to discharge (this is similar to the recovery outcome used in the ACTT-1 trial)
13. Time to discharge or being able to independently undertake usual activities with minimal or no symptoms
14. Time to being able to independently undertake usual activities with minimal or no symptoms (discharge status will be ignored)

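### Clinical organ dysfunction omits death and has no rule for it, and its final item weights are left to be developed from deaths at the end of the trial

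*SAP*

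**What the plan says.** Protocol 4.2 item 12 defines the outcome as new onset "of any one or more of the following conditions (or requirement for the following therapies) through Day 28", under respiratory, cardiac and vascular, renal, hepatic, neurological, hematological and infective headings. Death is not among the entries.

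SAP 7.4 carries the outcome over by name only ("4. Clinical organ dysfunction"). The analysis text gives it two forms:

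- Interim: "For interim analyses we will consider clinical organ dysfunction as a binary composite endpoint at Day 7 and Day 28". The logistic model stated for binary outcomes applies.
- Final: the severity of each dysfunction is to be reflected "by developing a weighting scheme by examining the pooled association of each item with subsequent death". There is no formula, time window, rule for sparse items or model for the resulting score.

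Mortality is a separate secondary outcome ("9. All-cause mortality through Day 28"). Secondary outcomes are analysed on complete cases, without multiplicity adjustment, as support for the primary analysis. The four key secondary outcomes named in SAP 1.4 do not include this one.

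On mortality, Protocol 5.5.3 says: "The study is not powered to detect treatment differences in mortality, because the mortality is expected to be low". SAP 1.4 repeats the expectation.

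**The concern.** Death prevents organ dysfunction from being observed and is also worse than any item on the list. An outcome that counts listed items and ignores death cannot separate a participant who recovered from one who died with no listed item. Early death also stops later items from accruing in that participant.

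Such deaths are plausible. Protocol 2.2.4 notes that patients who might otherwise be considered for intensive care "may be palliated if clinical services are overwhelmed". Item 12 also counts only new onset, and SAP 1.2.3 reports 10% of participants on high-flow oxygen at entry. If such a participant dies without further escalation or another listed condition, nothing on the list is triggered.

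The weighting adds a second problem. Death would set the value of every item while having no value of its own. The weights would be chosen after the data are complete, from a number of deaths that the plan expects to be small. At stake is whether this outcome's treatment comparison can be interpreted on its own terms.

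**Working it through.** The plan states no event rate, sample size or power for this outcome, so there is no figure to reproduce. The check compares the texts and then gives illustrations on stated assumptions.

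**1. Items (Protocol 4.2 item 12).** Respiratory 3 + cardiac and vascular 4 + renal 1 + hepatic 1 + neurological 3 + hematological 2 + infective 1 = 15. Deaths listed: 0.

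**2. How the plan treats death in other outcomes.**

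| Outcome | Rule for death |
|---|---|
| Primary ordinal scale (Protocol Appendix F) | Worst category, 7 |
| ACTT-like scale (SAP 7.4 item 5) | A category of its own, listed last |
| Hospitalization status (SAP 7.4 item 8) | Unfavorable |
| SAP 7.4 outcomes 11-14 | Competing risk |
| SAP 7.4 outcomes 15-17 | Value 0 |
| Clinical organ dysfunction (SAP 7.4 item 4) | None stated |

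**3. Score of a death without a listed event.** In the binary form, 0 of 15 items is no event. If the final score is a weighted sum of items (an assumption, since no formula is given), it is 0 whatever the weights. A participant who recovers without an event gets the same values. If the complete-case rule were instead read as dropping early deaths, they would still not count as a bad result.

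**4. What is hidden.** Analysis population 579 (SAP 4), taken as 289.5 per arm. Let *q* be the listed-event rate, equal in both arms, and *d* the rate of death without a listed event; all rates are assumed. The odds ratio is hIVIG versus placebo for a bad result, computed from *q* as written and from *q + d* if death counts.

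| *q* | *d*, hIVIG v placebo | Deaths | OR as written | OR counting death |
|---|---|---|---|---|
| 15% | 3% v 1% | 8.7 v 2.9 | 1.00 | (0.18/0.82)/(0.16/0.84) = 1.15 |
| 15% | 5% v 1% | 14.5 v 2.9 | 1.00 | (0.20/0.80)/(0.16/0.84) = 1.31 |
| 25% | 3% v 1% | 8.7 v 2.9 | 1.00 | (0.28/0.72)/(0.26/0.74) = 1.11 |
| 25% | 5% v 1% | 14.5 v 2.9 | 1.00 | (0.30/0.70)/(0.26/0.74) = 1.22 |
| 15% | 1% v 3% | 2.9 v 8.7 | 1.00 | (0.16/0.84)/(0.18/0.82) = 0.87 |

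A difference is hidden in either direction, harm or benefit.

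**5. Deaths available to set weights.** Table 1 gives 0.6% and 1.0% dead at Day 7, an average of 0.8%; 0.008 × 579 = 4.6 deaths. The supplied text gives no Day 28 rate for this population. Assumed rates of 2%, 5% and 10% give 11.6, 29.0 and 57.9 deaths, or 0.8, 1.9 and 3.9 per item when divided by 15. This ratio is only a rough guide: one death can follow several items, and each association uses all participants.

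**6. Precision and type I error of pooled weights.** I simulated 4,000 trials of 579 with no treatment effect. The 15 correlated items had assumed prevalences of 0.5% to 15%, with 37 deaths on average. Each weight was the pooled log odds ratio of death, with 0.5 added to each cell.

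- Mean weights ran from 2.27 to 3.58, a spread of 1.31.
- The standard deviation of a weight was 0.35 to 0.52 for items with prevalence 3% or more, 0.65 at 2%, and 0.89 to 1.00 at 1% or less.
- The two-sided 5% test of the weighted score rejected in 4.9% of trials (Monte Carlo standard error 0.3%).

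For the rarest items the noise in one weight is about three quarters of the whole spread between items (1.00/1.31 = 0.76). The test keeps its level because the weights ignore treatment assignment.

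**The case against.** The strongest reply is that a morbidity measure reported beside mortality is a legitimate choice. Deaths are not lost: they are category 7 of the primary scale, part of the key composite of categories 5-7, part of the primary safety composite through Day 7 and of SAE or death through Day 28, and outcome 9 on their own. The outcome is supportive and not key. All of this stands and limits the weight of the point. It does not make this outcome's own odds ratio interpretable when deaths without a listed event differ between arms.

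It is also fair to say that the palliation remark in Protocol 2.2.4 is background on intensive care thresholds. It does not describe this trial's participants. Many deaths would probably follow ventilation, vasopressors, high-flow oxygen, delirium or another listed item. The share that would not is unknown.

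A reader might infer more than the documents support:

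- *That the arm with more such deaths looks better.* With equal listed events the arms look the same (OR 1.00). The worse arm looks better only if its deaths displace listed events that would otherwise have been recorded, and nothing supplied quantifies that.
- *That data-derived weights inflate type I error.* Pooled weights ignore assignment, and the simulated rate was 4.9%.
- *That an item with no later deaths gets no weight.* No stated formula implies this.
- *That the SAP expressly codes these deaths as event-free.* It does not; that result follows from the definition because no rule is given.

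**Conclusion.** The point holds within limits. The omission of death from the list, and the absence of any rule for it in SAP 7.4, are plain on the text and out of line with how the plan treats death in the outcomes compared above. The consequence is a blind spot: in the illustrations, true odds ratios of 0.87 to 1.31 for death or dysfunction all appear as 1.00. Those figures rest on assumed rates of listed events and of deaths without one.

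The weighting is not pre-specified, and with few deaths it would be imprecise, most of all for rare items. That the weights come from this trial's own deaths is the natural reading of developing them at the end of the trial from a pooled association, though the SAP does not say so in so many words. The size of the imprecision depends on the assumed prevalences and on Day 28 mortality. SAP 1.2.5, listed in the contents as pooled follow-up results, was not in the text available here. Any Day 28 death count there should replace the assumed range.

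The change is worth making because it is cheap. The conclusion on the primary endpoint is unaffected.

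**What to change.** In SAP 7.4 item 4, before unblinding, define the analysed outcome as death or new clinical organ dysfunction, through Day 7 and through Day 28. Use the logistic model already stated for binary outcomes (treatment, entry category, product group). Report organ dysfunction alone by arm as a descriptive summary.

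If a weighted score is wanted:

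- give death the worst value;
- fix the weights and their source before unblinding, and state the model for the score;
- label it exploratory.

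Appendix F ranks alone cannot supply the weights. Hepatic decompensation, acute delirium, disseminated intravascular coagulation and severe infection do not appear there, and stroke spans categories 4 and 5.

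The binary option costs a sentence of SAP text and no new data, since deaths through Day 28 are already collected. Its downside is small: the headline result becomes organ dysfunction or death instead of organ dysfunction alone, which departs from the protocol's definition and gives up the severity grading the SAP hoped to add. The weighted option costs more, because weights for all 15 items must be agreed in advance.

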## 5 STUDY DESIGN

### 5.1 Overall Study Design

This study is an adaptive, randomized, double-blind, placebo-controlled trial to evaluate the safety, tolerability and efficacy of hIVIG in consenting hospitalized patients with COVID-19 who have had COVID-19 symptoms  $\leq 12$  days, and who do not have life-threatening organ dysfunction or organ failure. Remdesivir will be provided to participants in both the hIVIG and placebo groups as SOC unless contraindicated for an individual participant.

Participants may co-enroll in INSIGHT observational studies (e.g. INSIGHT 004 Genomics, FLU-003+) or have been previously enrolled in such studies prior to hospitalization (e.g. ICOS).

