**Time to discharge from hospital, time to the 2 most favorable categories of the primary ordinal outcome:** We expect that by Day 28, almost all participants will be discharged from the hospital. Similarly, we expect most participants will be in in one of the 2 most favorable categories of the primary ordinal outcome by Day 28. In the ACTT-1 trial, in the subset of participants who entered the trial with disease severity similar to our eligibility criteria (ACTT-1 ordinal outcome categories 4+5), 94.7% had been discharged from the hospital by Day 28. This percentage was similar for the ACTT-1 definition of “recovery” that include a small percentage of participants who were hospitalized but no longer requiring medical care. Comparing the hVIG versus placebo groups for time to hospital discharge, our study is powered to detect a relative rate ratio (RRR) of 1.3 with 80% power and a significance level of 0.05. The power calculations assume that the RRR is approximately constant to Day 28, the overall cumulative percentage discharged (pooled across treatment groups) by Day 28 is 94% and that between 2.5 and 3% withdraw consent or are lost to follow-up by Day 28. We assume power is similar for time to the 2 most favorable outcomes of the primary ordinal outcome.

**Hospitalization status:** Comparing the hVIG versus the placebo+SOC groups for the hospitalization status (a binary outcome, alive and discharged from the hospital to home or rehabilitation versus dead or hospitalized) on Day 7, the total sample size of 500 participants is sufficient to detect an increase in the proportion discharged to

58% in the hIVIG group from 45% in the placebo group (OR=1.7), with 80% power. Similarly, the study has 80% power to detect an increase to 81% in the hIVIG group compared with 70% in the placebo group (OR=1.85) at Day 14. Corresponding estimates from the ACTT-1 trial were 51% discharged on Day 7, and 77% on Day 14, for participants that were similar to ours and randomized to the remdesivir arm (confidential data; personal communication). Our hypothesized percentages are slightly lower, because our eligibility criteria allow for use of high-flow oxygen, in addition to the ACTT-1 ordinal categories 4+5. Power calculations assume that the treatment groups are compared by intent-to-treat.

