## APPENDIX F CLINICAL CATEGORICAL DEFINITIONS FOR ORDINAL OUTCOME

*Each participant is categorized in the highest applicable category.*

Ordinal Category	Categorical Description	Categorical Definition*
7	Death	Death
6	End-organ failure	Currently requiring invasive assisted ventilation, extracorporeal membrane oxygenation, mechanical circulatory support, vasopressor therapy or renal replacement therapy
5	Life-threatening end-organ dysfunction	Currently requiring non-invasive assisted ventilation or high-flow oxygen or Extra-pulmonary: Symptoms and signs of an acute stroke (NIHSS > 14)
4	Serious end-organ dysfunction	Currently requiring supplemental oxygen ( $\geq 4$ liters/min, or $\geq 4$ liters/min above premorbid requirements**) but not high-flow oxygen or Any of symptoms or signs of the following extra-pulmonary conditions: Stroke (NIH Stroke Scale/Score [NIHSS] $\leq 14$ ), meningitis, encephalitis, or myelitis, myocardial infarction, myocarditis, pericarditis, or New York Heart Association Class III or IV congestive heart failure, arterial or deep venous thrombosis including pulmonary embolism.
3	Moderate end-organ dysfunction	Requiring supplemental oxygen < 4 liters/min, or < 4 liters/min above premorbid requirements**
2	Limiting symptoms due to COVID-19	Symptomatic and currently unable to independently undertake usual activities
1	No limiting symptoms due to COVID-19	Can independently undertake usual activities with minimal or no symptoms

*\*Continued hospitalization or presence in a particular category of inpatient facility (e.g. intensive care or high dependency) is not used to divide these categories, as indication for continued hospitalization among recovering COVID patients is intrinsically subjective, in part determined by social and financial factors, and varies markedly across the globe.*

*\*\* Premorbid requirement refers to requirements prior to the development of COVID-19, for example in patients with chronic obstructive pulmonary disease, other chronic pulmonary diseases, or oxygen requirements related to altitude.*

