### 1.2.3 Summary of Baseline Characteristics

Selected baseline characteristics that were considered (as of March 23, 2021) in revising the SAP are given below.

1. As noted above, participants are from 11 countries. Numbers enrolled by country are: Denmark (77), Germany (10), Spain (65), Greece (70), UK (19), Indonesia (33), Argentina (4), Israel (6), Japan (15), Nigeria (41), and U.S. (253).
2. Median (25th, 75th percentile) of age is 59 (50, 70) years.
3. Median (25th, 75th percentile) of symptom onset is 8 (6, 10) days.
4. Oxygen status (above pre-COVID-19 requirement): 28% were not receiving oxygen; 34% were receiving < 4 L/min; 28% were receiving ≥ 4 L/min; and 10% were receiving high-flow oxygen.
5. 541 (93%) received remdesivir prior to randomization or on the same day as randomization as part of SOC.
6. 329 (56%) were receiving corticosteroids at entry; 48 (84%) among those on high-flow oxygen and 229 (62%) among those on supplemental oxygen.
7. 355 (60%) were receiving heparin (prophylactic, intermediate, or therapeutic dose) at entry.
8. Median (10th, 25th, 75th, 90th percentile) BMI is 29.8 (23.0, 25.8, 34.7, 40.2) kg/m^2.
9. Selected diagnoses (% reported) collected as part of a medical history and an elevated BMI are summarized below:
  - o Asthma (10%)
  - o Cerebrovascular event (1%)
  - o COPD (6%)
  - o Diabetes (28%)

- Heart failure (4.6%)
- Hepatic impairment (2%)
- HIV (2%)
- Hypertension requiring medication (42%)
- Immunosuppressive disorder other than HIV (1%)
- Malignancy (4%)
- MI (3%)
- Renal impairment (7%)
- BMI  $\geq$  30 kg/m^2 (49%)

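### About 10% of participants were already in category 5 at entry, and SAP 7.4 does not say how they enter the analysis of time to categories 5-7 (outcome 10)

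*SAP*

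**What the plan says.** SAP 7.4 lists outcome 10 as "Time to the three least favorable categories of the primary outcome measure", that is, categories 5, 6 or 7. The estimation rule for this outcome and for death reads: "the cumulative incidence of death (outcome 9) or the three least favorable categories (outcome 10) by treatment group will be estimated using Kaplan-Meier methods". A log-rank test compares the arms, and a Cox model supplies a summary hazard ratio. The paragraph ends by stratifying the models by product group and baseline ordinal group. It does not say whether this covers the log-rank test. For outcomes 11-14, by contrast, the SAP names both the test and the regression as stratified. SAP 7 makes the mITT population (579) the default.

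Protocol Appendix F defines category 5, labelled life-threatening end-organ dysfunction, as "Currently requiring non-invasive assisted ventilation or high-flow oxygen" or a severe acute stroke. Protocol 7.2 excludes non-invasive ventilation but does not list high-flow oxygen. Protocol 5.5.3 states that "our eligibility criteria allow for use of high-flow oxygen". SAP 1.2.3 reports that "10% were receiving high-flow oxygen" at baseline. Protocol 5.1 nevertheless describes participants as those "who do not have life-threatening organ dysfunction or organ failure", and SAP 1.4 says the same.

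**The concern.** A time-to-event analysis needs participants who are free of the event when the clock starts. A participant on high-flow oxygen at entry has already reached category 5, so a first occurrence of categories 5-7 records entry status and not what happened after the infusion. The visible text gives no at-risk restriction, no new-onset wording, no time origin and no tie method for outcome 10. The new-onset idea was available: protocol 4.2, item 12 (clinical organ dysfunction) uses it.

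The trial aims to prevent further progression. At stake are a curve that can be read as progression when part of it is baseline status, and a hazard ratio that depends on unstated software choices.

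**Working it through.** **Inputs.** From SAP 1.2.3: "48 (84%) among those on high-flow oxygen" (corticosteroid users). From SAP 1.2.2 and SAP 4: 593 randomised, 579 in the mITT population. The documents give no event rate, hazard ratio or power for outcome 10, so those below are assumptions.

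**1. Share in the event state at entry.** 48/0.84 = 57, and 57/593 = 9.6%, which reproduces the stated 10%. In the mITT population this is about 0.096 × 579 = 56; 10% of 579 is 58.

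**2. Kaplan-Meier curve, if entry status counts as a Day 0 event.** Displayed risk = p + (1 − p)r, where p = 0.0961 and r is the true 28-day risk in the rest. The share of events that is entry status is p divided by the displayed risk.

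| r | Displayed | Entry status as share of events |
|---|---|---|
| 10% | 18.6% | 52% |
| 15% | 23.2% | 41% |
| 20% | 27.7% | 35% |
| 25% | 32.2% | 30% |

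The curves are by treatment group, so stratifying the models does not change this.

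**3. Log-rank stratified by baseline category.** Take 28 of the 57 in one arm, all with the event at the same time.
- O − E = 28 − 57 × 28/57 = 0.
- Variance = 57 × (28/57) × (29/57) × (57 − 57)/(57 − 1) = 0.

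The stratum contributes nothing.

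**4. Cox stratified by baseline category.**
- Breslow ties: the score at HR = 1 is 0, but the information is 28 × 29/57 = 14.2. Weight is added at no effect.
- Efron ties: each step removes the same fraction of both arms, so the arm shares and the result are the same.
- Exact ties: when everyone fails at once only one configuration is possible, so the stratum adds nothing.
- Time-zero events dropped by the software: the stratum also adds nothing.

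A hand approximation for Breslow or Efron, with 58 entrants in category 5 (58/4 = 14.5 units), 521 others and true HR 0.65: events in the rest D = 260.5 × [r + 1 − (1 − r)^0.65], weight w = (D/4)/(D/4 + 14.5), and estimated HR = 0.65^w.

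| Placebo risk r | D | D/4 | w | HR by hand | HR simulated, stratified by baseline category |
|---|---|---|---|---|---|
| 12% | 52.0 | 13.0 | 0.47 | 0.82 | 0.82 |
| 18% | 78.4 | 19.6 | 0.57 | 0.78 | 0.77 |
| 25% | 109.6 | 27.4 | 0.65 | 0.75 | 0.76 |

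Without the category-5 entrants the simulated HR is 0.63-0.66. Adding stratification by product gives 0.81, 0.77 and 0.74. With other assumed effects and 28-day progression of 10-25%, a true 0.60 becomes 0.72-0.80 and a true 0.70 becomes 0.79-0.85.

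**5. Log-rank power by simulation (true HR 0.65).** Ranges are across repeat simulations with 56 to 58 category-5 entrants, whose events all fall on Day 1.

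| Placebo risk | Stratified, or entrants excluded | Unstratified, entrants kept |
|---|---|---|
| 12% | 31-34% | 15-21% |
| 18% | 46-50% | 32-34% |
| 25% | 57-61% | 43-48% |

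**The case against.** The strongest reply is that the SAP already stratifies by baseline ordinal group, so category-5 entrants are compared only with each other, and that the stated comparison is the log-rank test, not the Cox Wald test. This largely stands. If the stratification covers the log-rank test, that test loses nothing. It does not protect the curve, nor a Cox estimate that keeps the tied events under Breslow or Efron.

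A reader might infer that the hazard ratio is simply biased toward 1. The documents do not support that: it depends on the tie method and time origin, and the SAP states neither. A reader might also quote the Cox Wald power loss (33%, 45% and 58% falling to 9%, 25% and 40%) as the trial's loss. It belongs to a test that the SAP does not name for this comparison. Nor were these participants enrolled against the criteria, since protocol 5.5.3 says high-flow oxygen is allowed.

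Importance is also limited. Outcome 10 is not among the four key secondary outcomes in SAP 1.4, SAP 7.4 calls the secondary outcomes supportive, and clinical organ dysfunction already captures new-onset deterioration. The primary Day 7 analysis adjusts for entry category and is not touched by this point.

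**Conclusion.** The gap is real, and its consequence is conditional. About 57 participants (9.6%) are in the outcome 10 event state at entry, with no visible rule for them.

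- **Curve:** if entry status counts, each arm starts near 10%.
- **Hazard ratio:** an assumed 0.65 is reported as about 0.76 to 0.82, but only if the tied events are kept under Breslow or Efron ties.
- **Log-rank test:** unaffected if stratified by baseline category; power falls from roughly 32-60% to 15-48% if unstratified.

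The sizes rest on assumed placebo risks of 12-25% in the rest, the assumed hazard ratio, and all category-5 entrants having their event at one time. If the clock starts on Day 1, some may have left high-flow oxygen by then. The stratum would then measure failure to leave category 5, which is still not progression; that case was not simulated. SAP 1.2.5 (pooled follow-up results) is not in the text reviewed, so a rule there cannot be ruled out. For a supportive outcome this should be corrected, but no primary or key secondary conclusion depends on it.

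**What to change.** In SAP 7.4, outcome 10, before unblinding:

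- Analyse participants in categories 1-4 at entry (about 521 of 579, 90%).
- Report participants in category 5 at entry separately, with the event defined as first entry to category 6 or 7.
- State that the log-rank test is stratified by product group and baseline ordinal group, as the Cox model is.

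In the simulations, removing the category-5 entrants brought the Cox estimate back to the assumed value, and the curve then starts at zero. The cost is SAP wording and a main analysis covering about 90% of participants, with the rest shown alongside.

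Separately, the population description in protocol 5.1 and SAP 1.4 must be reconciled with protocol 5.5.3, Appendix F and SAP 1.2.3.
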